#### 7.3 Informed Consent

Written informed consent must be obtained for each study subject prior to the commencement of the study. The written informed consent (approved by the Institutional Ethics Committee/ REB) must be signed and dated by the investigator. A copy of the signed informed consent form will be given to the subject. The signed informed consent will be retained with the study records at the site. The investigator is responsible for assuring that informed consent is obtained regarding each subject in accordance with local guidelines and ISO14155 standard.

#### 7.4 Replacement of Dropouts

Subjects have the right to withdraw from the study at any time, for any reason, without jeopardizing their medical care. Subjects, who have not completed the 6-month follow-up visit and drop out of the study for any reason, may be replaced. Dropouts will be evaluated in the Intent to Treat (ITT) Cohort. A separate cohort will exclude these subjects. Every effort will be made to determine the reason for the subject dropping out of the study. Where possible, subjects will be followed for safety and encouraged to return for follow-up visits for any unresolved safety events.

# 8 Trial Procedures

# 8.1 Visit Schedule

#### 8.1.1 Screening and Consent

Potential participants will be provided with written information about the study describing the study, advising them of the study requirements, and possible risks. Study investigators must

**CONFIDENTIAL** - THIS DOCUMENT CONTAINS CONFIDENTIAL AND PROPRIETARY INFORMATION. THIS DOCUMENT MAY NOT BE REPRODUCED, USED, OR DISCLOSED TO ANY THIRD PARTY WITHOUT PRIOR WRITTEN CONSENT.

ensure that potential participants understand the information provided, and review requirements and potential risks. Individuals agreeing to participate in the study must sign the informed consent form according to local regulations. Upon verification of eligibility and execution of informed consent, subjects will be assigned a study code.

Screening visit will be performed up to 2 weeks before surgery and will include:

- Best Corrected Visual Acuity (BCVA)
- Slit Lamp Examination
- IOP will be measured either by tactile evaluation or using an appropriate tonometry technique
- OCT/UBM imaging
- Pain assessment with visual analogue scale (VAS)
- Concomitant medications
- Women of child-bearing potential must provide a negative pregnancy urine test.
- Subject demographic and medical information acquired from subject's medical file.

# 8.1.2 Implantation

Implantation day will be recorded as day 0; enrolment day Safety data will be collected upon enrolment.

Patients will be hospitalized as decided by the surgeon, estimated 1 hospitalization day will be required. Patients will be informed that they have the right to contact the PI or designee per their discretion

# 8.1.3 Operative Evaluation

During the procedure of each eye, most essential safety parameters, such as collapse and/or bleeding of the anterior chamber, iris or lens damage and unusual surgical problems will be recorded. Additionally, proper placement of the device's components (i.e. optic and skirt) will be confirmed and recorded.

#### 8.1.4 Procedural Failures

Failure to perform study device procedure will be recorded in the CRF as an operative failure.

#### 8.1.5 Post-Operative Supportive Care

Patients will be prescribed with prophylactic antibiotics and anti-inflammatory medications post implantation. Regimen for each medication and/or the addition of medications such as hypertension prophylaxis will be decided on a case by case basis and per the investigator's discretion.

The following options of treatment may be considered:

• A flouroquinolone, preferably 4th generation, should be applied for the first month QID(4Xd)

**CONFIDENTIAL** - THIS DOCUMENT CONTAINS CONFIDENTIAL AND PROPRIETARY INFORMATION. THIS DOCUMENT MAY NOT BE REPRODUCED, USED, OR DISCLOSED TO ANY THIRD PARTY WITHOUT PRIOR WRITTEN CONSENT.

If antibiotics are unavailable, 1% povidone iodine 2 to 4 times daily can be used for the short-term.

• To control inflammation after KPro implantation, prednisolone 1% drops 2-4x per day for the first month are recommended either with or without additional non-steroidal anti-inflammatory drugs (NSAID) such as Tromethamine.

Patients will be advised to avoid eye rubbing since infectious or toxic debris may be pushed into the eye and will be instructed to wear sunglasses or UV-blocking contact lenses to protect against UV induced eye damage.

# 8.1.6 Follow Up

Follow Up- (up to 12 months) visit schedule: One day post op, one week ( $\pm$ 2 days) one month ( $\pm$ 7 days), two months ( $\pm$ 14 days) three months ( $\pm$ 14 days), six months ( $\pm$ 14 days), nine months ( $\pm$ 14 days) and twelve-months ( $\pm$ 14 days) post-surgery.

On each follow-up visit, subjects will be subjected to the following examinations: (i) slit-lamp biomicroscopy, (ii) visual acuity (BCVA), (iii) IOP, (iv) concomitant medications record, (v) Pain assessment and (vi) Adverse events recording.

In every follow up visit, IOP will be measured by tactile assessment as follows: Digital palpation of the globe will be performed with the patient gently looking down. Palpation directly over a glaucoma drainage device plate should be avoided in patients with tubes who should be instructed to look in an alternate direction. The eye should then be very gently balloted between the surgeon's two index fingers, as his or her other fingers rest against the face and orbital rim.

In addition, OCT/UBM imaging will be performed on screening visit, on 1-week post-op and every 3 months starting at 3 months post-surgery.

During all study period only safety data (i.e. possibly related or related AEs, SAEs, UADE) will be collected in the eCRF for visits performed outside of protocol visits timetable.

# 8.2 Table Of Assessment

Assessments/Procedur es	Screening	Proce dure	Follow-up (time post surgery)			y)				
Time in study	-14 to -0	0	1 day	1 week ±2 days	1 month ±1 week	2 months ±2 weeks	3 months ±2 weeks	6 Months ±2 weeks	9 Months ±2 weeks	12 months ±2 weeks
Informed consent	Х									
Inclusion /exclusion criteria	х									
Medical history, Demographic, pregnancy test (women of child- bearing potential only)	x									
CorNeat KPro device implantation		х								
Slit Lamp Examination, BCVA, IOP	x	x	х	х	х	х	х	x	х	х
OCT/UBM imaging	X (Anterior)			X (RNFL)			X (RNFL)	X (RNFL)	X (RNFL)	X (RNFL)
Pain Assessment (Visual analogue scale- VAS)	x	x	x	х	x	x	x	x	x	x
Concomitant medications	x	х		x	x	x	x	x	x	x
AE/SAE/UADE		х	x	x	х	X	x	x	x	x

Only safety data will be collected in CRF for Post hospitalization period and visits performed between protocol scheduled visits (i.e., related or possibly related AE, SAEs, UADE)

#### UNCONTROLLED WHEN PRINTED

# 9 Training

CorNeat KPro implantation will be performed only by ophthalmic surgeons which are well trained in corneal surgery specifically keratoprosthesis implantations. Each ophthalmologist will be trained by implanting the CorNeat KPro implant in ex-vivo animal eyes prior to subject enrollment. Prior to the wet lab training, a presentation outlining the procedural step with an indepth discussion on the unique aspects of the device and procedure will be conducted. The Investigator formal training will be performed by the study sponsor prior to subject enrolment at the study center. Training certificate will be issued to investigators who successfully passed the wet lab.

# **10 Safety Parameter**

# **10.1** Adverse Event Definition

An adverse event is any undesirable or unintentional event that occurs during the course of the study, whether or not considered related to the device. Regardless of severity or relationship to the investigational device, all adverse events occurring during the study must be recorded in the subject's CRF

All adverse events will be coded using the Medical Dictionary for Regulatory Activities (MedDRA, most updated version) terminology and presented in tables by System Organ Class (SOC) and Preferred Term (PT).

AE data will be listed individually and summarized by SOC and by PT within a system organ class.

Additional tables will present adverse events by PT, SOC and severity and by relatedness to study device.

# 10.2 Severity of an Adverse Event

# Mild Adverse Event

A mild adverse event is one that its symptoms are barely noticeable to the subject. It does not influence performance, require drug treatment or prevent the subject from carrying on with normal life activities.

# Moderate Adverse Event

A moderate adverse event is one that its symptoms make the subject uncomfortable and causes some impairment to normal life activities. Treatment for the symptom(s) may be required.

#### Severe Adverse Event

A severe event is one in which the symptoms cause severe discomfort to the subject and limits the subject's normal life activities. Treatment for the symptom(s) may be required.

**CONFIDENTIAL** - THIS DOCUMENT CONTAINS CONFIDENTIAL AND PROPRIETARY INFORMATION. THIS DOCUMENT MAY NOT BE REPRODUCED, USED, OR DISCLOSED TO ANY THIRD PARTY WITHOUT PRIOR WRITTEN CONSENT.

# 10.3 Relationship to Study Device

The following definitions will be used to assess the relationship between an adverse event and the investigational device.

### Not Related

The event is clearly related to other factors such as the subject's clinical state, therapeutic interventions or concomitant drugs.

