# 5.2 Endpoints

# 5.2.1 Primary Safety Endpoint

The frequency and severity of all unanticipated adverse device-related events (UADE) or treatment-related adverse events, during and after implantation of the CorNeat KPro device up to 12 months should be less than SOC (as detailed in section Known Potential Risks).

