### Possibly Related

The event has a reasonable temporal relationship to the use of the investigational device and follows a known response pattern to the investigational device. However, a potential alternate etiology may be responsible for the event. The effect of device withdrawal is unclear. Re-challenge information is unclear or lacking.

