- Retro-KPro membranes (RPM) formation- are the most common complication in KPro implanted patients, with an incidence of 27-47.6%.

RPM is usually treated with Nd:YAG membranotomy which can cause retinal detachment in 26.7%.

• Endophthalmitis - The incidence of endophthalmitis in KPro patients is relatively high (1.2-11.4%) even in patients with prophylactic antibiotic topical treatment.

Other risks include:

- Transient inflammatory reaction around the eye
- Vitreous hemorrhage- bleeding inside the eye
- Vitritis- sterile inflammation inside the eye
- Retinal Detachment- separation of the retina from the wall of the eye resulting in loss of vision
- Ptosis- a droopy eyelid
- Foreign body sensation

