# 10.11 Premature Termination or Suspension of the Study

The trial will be stopped if severe side effects or infections, resulting in device removal and related with the investigational device, are diagnosed in three patients.

In case of premature termination of the study, the PIs will decide regarding the required future follow up for each patient on a case by case basis.

The trial may be temporarily suspended if there is sufficient reasonable cause.

Circumstances that may warrant termination or suspension include, but are not limited to:

• Determination of unexpected, significant, or unacceptable risk to participants

**CONFIDENTIAL** - THIS DOCUMENT CONTAINS CONFIDENTIAL AND PROPRIETARY INFORMATION. THIS DOCUMENT MAY NOT BE REPRODUCED, USED, OR DISCLOSED TO ANY THIRD PARTY WITHOUT PRIOR WRITTEN CONSENT.

- Demonstration of poor efficacy that would warrant stopping
- Insufficient compliance to protocol requirements
- Data that are not sufficiently complete and/or evaluable

If the study is suspended, the PIs will promptly inform the EC and will provide the reason(s) for the suspension. Study may resume once concerns about safety, protocol compliance, and data quality are addressed and satisfy the sponsor, EC, and /or respective regulatory agency.

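### A device-only causality scale and an undefined treatment-related endpoint can remove harms from the primary safety count that the 10.8 benchmark includes

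*Protocol*

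**What the plan says.** **Causality scale.** Protocol 10.3 gives definitions "to assess the relationship between an adverse event and the investigational device". Its Not Related category reads: "The event is clearly related to other factors such as the subject's clinical state, therapeutic interventions or concomitant drugs". Possibly Related asks for a reasonable time relation and a known response pattern to the device, and adds: "However, a potential alternate etiology may be responsible for the event". No other causality rating exists. The CRF items in 10.6 and the listings in 12.2.3 carry relationship to the device alone.

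**Endpoint.** Section 5.2.1, repeated in the Synopsis, sets the primary safety endpoint as "The frequency and severity of all unanticipated adverse device-related events (UADE) or treatment-related adverse events, during and after implantation", to 12 months, and requires it to be below SOC as given in 10.8. Treatment-related is not defined anywhere. Section 12.2.3 says that no separate SAP is in use, so the definition has no other home.

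**Drugs and procedures that come with the implant.** Section 8.1.5 has antibiotics and anti-inflammatory drugs prescribed after implantation, for example: "To control inflammation after KPro implantation, prednisolone 1% drops 2-4x per day for the first month are recommended". Sections 10.8 and 10.9.1 expect laser or surgical treatment of retroprosthetic membrane (RPM), and intravitreal injection or vitrectomy for infection.

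**Benchmark.** Section 10.8 gives RPM in 27–47.6% of keratoprosthesis patients and continues: "RPM is usually treated with Nd:YAG membranotomy which can cause retinal detachment in 26.7" per cent. It also gives raised intraocular pressure (IOP) in 19–38%.

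**Recording.** Section 10.1 requires every adverse event in the CRF, whatever its relationship. At off-schedule visits, 8.1.6 and the note under the table in 8.2 collect only related or possibly related events, SAEs and UADEs.

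**The concern.** Many of the therapeutic interventions and concomitant drugs in this trial are given because the eye received the device. A detachment clearly caused by laser treatment of an RPM, or a pressure rise clearly caused by the steroid drops, meets the wording of Not Related, yet neither would have arisen without the implant.

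What is at stake is the like-for-like character of the primary safety comparison. If the trial's numerator passes through 10.3 and the benchmark does not, the trial can come out below the benchmark because of coding. With 10 subjects and one eye each, recoding a single eye moves a percentage by 10 points.

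**Working it through.** The protocol derives no figure on this point. Its 10 subjects rest on regulatory precedent, with no alpha, power or effect size, so there is nothing to reproduce. The check is mainly one of text, with arithmetic for scale.

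**Step 1: can such a harm enter the endpoint?** There are two routes.
- UADE: 10.5 excludes effects already identified in 10.8 in nature, severity or degree of incidence. Section 10.8 lists retinal detachment twice, as a harm of the laser and among the other risks, so this route is largely closed.
- Treatment-related: the term is undefined, and the only rating collected is to the device. An analyst who uses the available field counts device-related events. A harm clearly due to a drug or a rescue procedure then scores zero.

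**Step 2: does the benchmark contain these harms?** For the laser it does, explicitly (26.7%). For IOP, 10.8 states no exclusion of drug-caused cases. Whether the cited studies made one cannot be seen from the protocol.

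**Step 3: scale for the laser example.** Inputs from 10.8: RPM 0.27 to 0.476; detachment after Nd:YAG 0.267. Assumption: every RPM is lasered (the protocol says only that this is usual).
- Rate per eye: 0.27 × 0.267 = 0.072; 0.476 × 0.267 = 0.127.
- Expected in 10 eyes: 0.72 to 1.27.
- P(at least one) = 1 − (1 − p)^10: 1 − 0.928^10 = 0.53; 1 − 0.873^10 = 0.74.
- If half of RPM eyes are lasered: p = 0.036 to 0.064, expected 0.36 to 0.64, P(at least one) = 0.31 to 0.48.

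**Step 4: effect on the comparison.** Suppose one of 10 eyes detaches after laser. Counted regardless of cause, the rate is 1/10 = 10%, above the lower derived benchmark (7.2%) and below the upper (12.7%). Counted through 10.3 as Not Related, it is 0/10 = 0%, below both.

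**Step 5: the drug example.** The IOP benchmark of 19–38% corresponds to 1.9 to 3.8 of 10 subjects. The protocol does not say what share is due to drugs, so no drug-specific count can be given.

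**Step 6: recording.** A non-serious pressure rise found at an unscheduled visit and attributed to the drops would be Not Related. Section 10.1 requires it in the CRF; 8.1.6 and the 8.2 note do not collect it there. The rating can thus decide whether the event is in the data at all.

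**The case against.** A reader might infer that 10.3 by itself removes these harms from the primary endpoint and from the stopping count, and that a site must code a post-laser detachment as Not Related. The protocol does not support that much.

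- **Endpoint.** The wording "unanticipated adverse device-related events (UADE) or treatment-related adverse events" is wider than device-related. Post-operative drugs and rescue surgery fit naturally under treatment, and nothing says that 10.3 decides the matter. This stands: exclusion follows only if the term is read as device-related. But nothing directs the wider reading either, and no data field supports it.
- **Coding.** Not Related applies only where the other cause is clear. A detachment after laser for a device-caused membrane has both device and procedure in its causal chain, so a site could argue for Possibly Related. This stands in part, because that category also needs a known response pattern to the device.
- **Stopping rule.** Section 10.11 counts only events "resulting in device removal and related with the investigational device". Neither a post-laser detachment nor a steroid pressure rise is among the explantation scenarios of 10.9.1, and an underlying RPM, infection or necrosis can still be rated related. The effect there is at most narrow.
- **Existing safeguards.** All adverse events are to be recorded, listed and tabulated, SAEs reach the sponsor whatever their relationship, and a DSMB reviews the data. So the harms are mostly visible, apart from the gap at off-schedule visits. Visibility in listings does not settle which events enter the comparison with SOC.
- **Size.** The 53–74% is a ceiling. It assumes that every RPM is lasered and every detachment is rated clearly procedural.

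**Conclusion.** The concern holds as a conditional defect. The only scale is to the device, its Not Related category has no exception for surgery, protocol drugs or rescue procedures, and the endpoint term that might bring these back is undefined. Read through 10.3, the trial's count omits a type of harm that 10.8 names in the benchmark, and the comparison tilts toward the device. Separately, 8.1.6 and the 8.2 note contradict 10.1 on what is collected at off-schedule visits.

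For scale, 0.7 to 1.3 laser-related detachments would be expected in 10 eyes if every RPM is lasered, and about half that if half are. These are rates from other devices, with no stated time horizon, and are not 12-month forecasts for this one. The protocol does not show that misclassification will occur, that all the benchmark rates are unfiltered, or that the stopping count is materially affected. The clinical stopping threshold is not in question.

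**What to change.** 1. In 5.2.1 and the Synopsis, define treatment-related as related to any of: the device, the implantation procedure, medication given under 8.1.5, or a procedure done to treat a device complication.
2. In 10.3 and 10.6, rate these four relationships separately. Do not force such events to at least Possibly Related to the device: that would turn, say, an allergy to an antibiotic drop into a device effect and merge distinct causes.
3. Make the comparison with 10.8 on each event named there, in all implanted eyes, regardless of attributed cause.
4. Reconcile 8.1.6 and the 8.2 note with 10.1, so that all adverse events are collected at off-schedule visits.

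The cost is a protocol amendment, a few more rating fields in the eCRF and one more table. No subjects or visits are added. The reported event rate may be somewhat less favourable to the device.

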### Possibly Related

The event has a reasonable temporal relationship to the use of the investigational device and follows a known response pattern to the investigational device. However, a potential alternate etiology may be responsible for the event. The effect of device withdrawal is unclear. Re-challenge information is unclear or lacking.

#### Related

The event follows a temporal sequence from the time of use of the device and follows a known response pattern to the investigational device and either occurs immediately following investigational device use, or improves on stopping the use of the device, or reappears on repeat exposure to the device.

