### **10.4** Serious Adverse Event Definition

A serious adverse event is an event that is: (a) fatal, (b) life-threatening (c) results in persistent or significant disability/incapacity (d) requires or prolongs in subject hospitalization or (e) leads to a congenital anomaly or birth defect.

Life threatening is defined as an event in which the subject is at risk of death at the time of the event. It does not refer to an event that hypothetically might have caused death if it was more severe.

Disability is defined as a substantial disruption of a person's ability to conduct normal life functions.

An unexpected adverse event is one that has not been previously observed or one that is a specificity or severity not consistent with the current investigator brochure.

All pre-existing medical conditions will be recorded on medical history or physical exam case report forms.

Hospitalization or prolonged hospitalization for diagnostic or elective procedures for pre-existing conditions will not be considered as SAE. Exceptions of adverse device effects are changes related to the underlying disease or medical conditions that are consistent with expected disease progression and will not be considered adverse device effects in this study.

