#### 10.5 Unanticipated Adverse Device-related Event Definition

An unanticipated adverse device-related event is any serious adverse effect on health or safety, any life-threatening problem or death caused by, or associated with a device, if that effect, problem, or death was not previously identified in nature, severity, or degree of incidence in section Known Potential Risks.

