# 10.6 Adverse Event Reporting

When an adverse event occurs, the following information and assessments in the adverse event section of the CRF will be recorded:

- The signs, symptoms or diagnosis of the event
- The date and time of onset and termination of the event (24-hours clock format where midnight is 00:00 and noon is 12:00)
- The adverse event severity using the criteria outlined above
- The relationship of the event to the investigational device as outlined above
- A description of any action taken regarding study device disposition
- A list of any required therapy, medication, treatment or diagnostic procedure
- Clinical behavior prior to the event, such as nutrition, medicine, physical activity etc.
- Any additional data which might be relevant to the event

The investigator is responsible for the appropriate medical management of all adverse events and for the personal safety and well-being of the subjects.

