# 10.7 Serious Adverse Events Reporting and Unanticipated Adverse Device-Related Events (UADE)

Any serious and/or unexpected and/or device related adverse event must be reported to the sponsor- CorNeat Vision and the Clinical Study Monitor via the EDC system. Full details of the event, treatment, and an assessment of the relationship between the investigational device must be provided in the report. The report shall be prepared by the principal investigator. Reports relating to the subject's subsequent medical course must be submitted to the sponsor until the event has subsided or, in case of permanent impairment, until the event stabilizes, and the overall clinical outcome has been ascertained.

CorNeat Vision will notify all investigators in writing of severe/serious or unexpected adverse events when this information is of global importance to subject safety and welfare. Reporting to the EC/REB will be done according to local regulation.

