### 10.8 Known Potential Risks

Known risks from usage of similar artificial corneas are:

- Postoperative Corneal Melt is one of the most severe complications that can occur after keratoprosthesis surgery with incidence of up to 30%. It may lead to scarring, irregular astigmatism, photophobia, decreased vision, and even endophthalmitis.
- Lack of graft retention Corneal grafts tissue artificial integration is limited and with time the bond between the implant and eye weakens. E.g. Boston KPro's retention rates decreases over time with incidence of lack of retention of 6, 11 and 25% after 1, 2- and 5-years post-op, respectively.
- Post-operative Glaucoma is the most important threat to long-term preservation of vision following Boston KPro surgery with elevation of intraocular pressure in 19–38 % of patients postoperatively and progression of pre-operative glaucoma in 7–14 % of patients. Development of glaucoma de novo following Kpro placement has been reported in 2-28% of KPro recipients .
- Poor post-operative visual quality Eyes with current KPros have very limited visual field and poor visual function. About 50% of patients implanted with Boston KPro maintain 20/200 CDVA after 8 years from surgery .

<sup>6 Bouhout, S., Robert, M.C., Deli, S. and Harissi-Dagher, M., 2018. Corneal melt after Boston keratoprosthesis: Clinical presentation, management, outcomes and risk factor analysis. Ocular immunology and inflammation, 26(5), pp.693-699.

<sup>7 Schaub, F., Bachmann, B.O., Seyeddain, O., Moussa, S., Reitsamer, H.A. and Cursiefen, C., 2017. Mid-and longterm experiences with the Boston-keratoprosthesis. The Cologne and Salzburg Perspective. Klinische Monatsblatter fur Augenheilkunde, 234(6), p.770.

<sup>8 Jin, B. and Zhu, X., 2017. The pathogenesis and prevention of corneal graft melting after keratoplasty. J Clin Ophthalmol, 1(1), p.10.

<sup>9 Ciolino, J.B., Belin, M.W., Todani, A., Al-Arfaj, K., Rudnisky, C.J. and Boston Keratoprosthesis Type 1 Study Group, 2013. Retention of the Boston keratoprosthesis type 1: multicenter study results. Ophthalmology, 120(6), pp.1195-1200.

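### Section 10.3 has no relatedness grade for a novel event in a first-in-human study, the endpoint's treatment-related events are not mapped to its grades, and the off-schedule recording rule contradicts 10.1

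*Protocol*

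**What the plan says.** Protocol 10.3 offers three grades of relationship to the device.

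- **Related:** the event has a temporal sequence from device use, and it "follows a known response pattern to the investigational device and either occurs immediately following investigational device use", or improves when use stops, or returns on repeat exposure.
- **Possibly Related:** this grade applies if it "has a reasonable temporal relationship to the use of the investigational device and follows a known response pattern to the investigational device", with another cause potentially responsible and withdrawal or re-challenge information unclear or lacking.
- **Not Related:** "The event is clearly related to other factors", with therapeutic interventions among the examples.

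There is no grade for unknown or unassessable. Section 10.6 requires, for each event, "The relationship of the event to the investigational device as outlined above".

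The study is first-in-human (section 6). The only risk list in the protocol, 10.8, opens with "Known risks from usage of similar artificial corneas are". It describes other devices.

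The primary safety endpoint (5.2.1 and synopsis) counts UADEs or treatment-related adverse events, during and after implantation, up to 12 months. The term treatment-related is not defined. Section 12.2.3 lists relationship to the device only, and says that no separate SAP is in use.

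On recording, 10.1 requires all adverse events in the CRF whatever their severity or relationship. Section 8.1.6 limits the eCRF, for visits outside the timetable, to possibly related or related AEs, SAEs and UADEs. The 8.2 footnote repeats that limit and adds the period after hospitalization.

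**The concern.** A first-in-human safety study exists largely to find response patterns that nobody has yet seen. A relatedness scale that asks for a known pattern before an event can be called even possibly related suits an established product. Here an investigator faced with a new, temporally plausible event must pick a grade that does not fit, and two investigators may pick differently.

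That choice carries through to the tables by relatedness and to the treatment-related part of the primary safety endpoint. The endpoint has a second weakness of its own: nothing says whether Possibly Related events count, or whether a complication of the surgery counts when the scale grades the device alone.

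The recording conflict is a separate matter. Sites cannot follow both 10.1 and 8.1.6 for a non-serious event judged unrelated and seen at an unscheduled visit.

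**Working it through.** The document states no figure on this point, so the check is of the definitions.

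**1. The gap in 10.3.** Take an event with a plausible time relation, no known response pattern to this device, and no clear other cause.

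- Not Related fails, because it needs a clear other cause.
- Possibly Related fails, because it needs a known pattern.
- Related fails, because it needs a known pattern.

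The remaining attributes do not rescue it. Vary other cause (none or potential) and supporting evidence of immediate onset, withdrawal or re-exposure (present or absent): 2 × 2 = 4 combinations, and all 4 fit no grade. Both device grades fail on the pattern condition alone.

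**2. Overlap in 10.3.** A known-pattern event with immediate onset, a potential other cause and no withdrawal or re-challenge information satisfies both Possibly Related and Related. Nothing says which prevails.

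**3. Against 10.5.** A UADE is a serious event "caused by, or associated with a device" that 10.8 had not identified in nature, severity or degree of incidence. If it is unanticipated in nature, it can hardly follow a known pattern. Read literally, the protocol can call it device-related in 10.5 and has no matching grade in 10.3.

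**4. Mapping to the endpoint.** The endpoint runs from the operation onward, and 10.8 includes intraoperative haemorrhage and vitreous prolapse. The scale in 10.3, the record in 10.6 and the listings in 12.2.3 address the device only. Because therapeutic interventions are an example of another factor, a surgical complication could be read as Not Related.

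**5. Recording.** 10.1: all events, any relationship. 8.1.6 and the 8.2 footnote: a subset chosen by relatedness, plus SAEs and UADEs. The difference is non-serious events graded Not Related or left without a grade.

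**6. Check of a replacement scale.** Use three yes/no questions: time relation plausible (T), clearly due to another cause (C), an alternative at least as likely (A). This gives 2³ = 8 combinations.

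- Not Related if T is no (4), or T is yes and C is yes (2): 6.
- Possibly Related if T yes, C no, A yes: 1.
- Related if T yes, C no, A no: 1.

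6 + 1 + 1 = 8, so every combination falls in exactly one grade.

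**7. Scale.** With 10 subjects, one subject classified differently moves a subject-level percentage by 1/10 = 10 points. Section 7.4 allows replacement of dropouts and 12.2.3 puts all enrolled patients in the safety set, so the denominator may exceed 10 and the step be smaller.

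**The case against.** The strongest reply is that the protocol has other nets. Serious novel events enter the endpoint through 10.5 without reference to 10.3. Section 10.4 says that "An unexpected adverse event is one that has not been previously observed" (or one inconsistent with the investigator brochure), and 10.7 says "Any serious and/or unexpected and/or device related adverse event must be reported" to the sponsor through the EDC, with no restriction by visit. Adverse events are also recorded at every scheduled visit, and all events are listed individually. A novel event has no rate in 10.8, so no comparison with a listed rate changes. All of this stands, and it confines the point. It does not supply a grade, and it does not settle which events count as treatment-related.

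Four stronger readings are tempting and are not supported.

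- *Novel events are lost under 8.1.6.* An event not previously observed has the 10.7 route. The conflict with 10.1 bears on non-serious events judged unrelated, which the endpoint would not count anyway and which may still be recorded at the next scheduled visit.
- *The footnote switches off recording for most of follow-up, because hospitalization is estimated at one day.* The same table marks adverse events at every scheduled visit.
- *Late complications in general cannot be graded.* Possibly Related needs only a potential other cause, which the eligible diagnoses will often supply, and explantation or replacement under 10.9.2 can give withdrawal or re-exposure information. Any gap for late known-pattern events is narrow.
- *The stopping rule in 10.11 is shown to misfire.* Its word related is not tied to 10.3, and no share of misgraded events can be derived.

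The investigator brochure may describe further patterns. It is not at hand, and it cannot describe a pattern that has yet to be seen.

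**Conclusion.** The point holds and should be fixed. As written, 10.3 leaves a temporally plausible event with no known pattern and no clear other cause without a grade, while 10.6 demands one. Treatment-related in the primary safety endpoint is not mapped to the grades. Sections 8.1.6 and 8.2 (footnote) contradict 10.1.

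The effect is on grading, on tables by relatedness, on the non-serious part of the treatment-related count, and on complete recording of non-serious events judged unrelated. The size of any miscount cannot be derived from the protocol.

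The conclusion rests on two assumptions: that 10.3 is applied as worded, and that known patterns of similar devices in 10.8 are not silently taken as patterns of this one. If they were, events of a kind listed in 10.8 could be graded, but a new kind of event still could not. Since 12.2.3 says that there is no SAP, the repair belongs in the protocol.

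**What to change.** - **10.3:** remove the known-pattern condition from Possibly Related and Related. Keep withdrawal or re-exposure information as supporting evidence only. Make the categories exhaustive and mutually exclusive, for instance by the three questions in step 6, so that a temporally plausible event without a clear other cause is at least Possibly Related.
- **10.6:** keep the device grade and record relationship to the implantation procedure as a second, separate grade. Do not merge the two. The procedure should not serve as an other factor that makes an event not treatment-related.
- **5.2.1 and synopsis:** state that treatment-related means graded Related or Possibly Related to the device or to the procedure. This is the conservative choice, and it should be written down before data are reviewed.
- **8.1.6 and the 8.2 footnote:** reconcile with 10.1 so that all adverse events are recorded.
- **10.11:** state how its word related corresponds to the 10.3 device grade. The two sections must be reconciled; no change to the rule is proposed here.

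The cost is protocol and eCRF wording and one extra eCRF field. More events will be recorded and more will count as treatment-related. How many cannot be derived, and over 12 months of ocular follow-up it may be more than a few.
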